5.6 Time and Events Table

	Screening / Baseline	Treatment		Follow	v-up Phase
Procedures		Every Cycle (Every 4 weeks)	End of Treatment ⁹	End-of- Study Visit	Survival
Frocedures	Within 4 weeks of Day 1	Cycles 1, 2, 3, 4, 5, 6 (Weeks 0, 4, 8, 12, 16, 20)	End of Week 24 (+ 7 days)	30 days after treatment	Follow-up Every 6 months for 36 months (+/7 days)
		Day 1 (+/- 7 days)		termination (+/- 7 days)	(// 22,5)
Informed Consent	x				
Eligibility review	Х				
Pregnancy test	Х				
Demographics	Х				
Medical / Surgical History	X				
Complete Physical Exam	Х	Х		Х	Х
Standard of Care CT imaging		As per standard of care, approximately every 8 weeks			
Height	X				
Weight	Х	X		Х	Х
Vital Signs	Х	X		X	X
Performance Status (ECOG or Karnofsky)	x	X		X	X
Adverse Event Assessment	Х	х	Х	х	
Concomitant Medications	Х	х		х	
Blood collection (CBC, CMP)	Х	х		Х	
CMP add-ons (Phos, Mag)		X (C1D1 only)			

	Screening / Baseline	Treatment		Follow	/-up Phase
Dragodiuse		Every Cycle (Every 4 weeks)	End of Treatment ⁹	End-of- Study Visit	0
Procedures	Within 4 weeks of Day 1	Cycles 1, 2, 3, 4, 5, 6 (Weeks 0, 4, 8, 12, 16, 20)	End of Week 24 (+ 7 days)	30 days after treatment	Survival Follow-up Every 6 months for 36 months (+/7 days)
		Day 1 (+/- 7 days)		termination (+/- 7 days)	, ,
CA 19-9 (biomarker)		X		х	
C-reactive protein (CRP)		X (C1D1 only)			
Fat soluble vitamin levels ⁵	Х			Х	
Research Blood Tests		X ¹		Х	
Stool Sample Microbiome and Stool Survey		X (C1D1 ⁷ and C3D1 ⁸ only)			
Fecal elastase	X ⁷				
Hand grip and 15 ft walk test		X ¹		Х	
Bionutrition assessment: ASA-24 (24-hour food recall) ³ ; taste and smell alteration		X (C1D1 and C3D1 only)		Х	
Self-administered QOL survey: PROMIS-29; FAACT		X ¹		Х	
Pancreaze treatment		X (daily) ⁶			
Self-reported daily Pancreaze accountability log and compliance calculation ⁴		х			
Physical Activity: Assess wearable activity monitor functionality		Х		Х	
Wearable activity monitoring			Continuous	S	X ²
Return research pill bottles/transition to SOC enzymes			Х		

	Screening / Baseline	Treatment		Follow	/-up Phase
Dresselves		Every Cycle (Every 4 weeks)	End of Treatment ⁹	End-of- Study Visit	0 000
Procedures	Within 4 weeks of Day 1	Cycles 1, 2, 3, 4, 5, 6 (Weeks 0, 4, 8, 12, 16, 20)	End of Week 24 (+ 7 days)	30 days after treatment	Survival Follow-up Every 6 months for 36 months (+/7 days)
		Day 1 (+/- 7 days)		termination (+/- 7 days)	(177 days)
Survival Follow-up					×

¹To be completed at baseline and day 1 of every other cycle for 6 months. 8 hour fast is required for all research blood draws, blood draws must be scheduled in the morning, and deviations must be recorded. ²Fitness tracking with the wrist-worn wearable activity monitor is optional during follow-up.

5.7 Removal of Subjects from Study

Patients can be taken off the study treatment and/or study at any time at their own request, or they may be withdrawn at the discretion of the investigator for safety, behavioral or administrative reasons. The reason(s) for discontinuation will be documented and may include:

³ASA-24 is completed electronically and may be completed within 7 days of the visit.

⁴Subjects will complete a daily compliance diary for the first two cycles only. Diary will be given to patients on Day 1 of the first two cycles. Subjects will return diary to study staff for compliance calculation on completion of each of the first two cycles.

⁵Fat-soluble vitamin labs to be drawn include: Vitamin A: serum retinol; Vitamin D:25-Hydroxy; Vitamin E: serum alpha-tocopherol; Vitamin K: PIVKA-II and prothrombin time.

⁶The patients will be followed on treatment for the 24-week study treatment period. Treatment may continue beyond the study treatment period, at the physician's discretion, per standard of care. Pancreaze will be dispensed at C1D1 and C4D1, and subjects will return remaining supply at C4D1 and the end-of-treatment visit for drug accountability by Research Pharmacy.

⁷Stool sample may be collected during screening or until C1D1 + 7 days.

⁸ Window for C3D1 sample is +/- 7 days.

⁹Subjects will continue to take the study drug until the Cycle 6 Day 28 time point. Subjects should be reminded to discontinue study supply of Pancreaze following Cycle 6 Day 28.

- **5.7.1** Patient voluntarily withdraws (follow-up permitted);
- **5.7.2** Patient withdraws consent (termination of treatment and follow-up);
- **5.7.3** Patient is unable to comply with protocol requirements;
- **5.7.4** Patient experiences toxicity that makes continuation in the protocol unsafe;
- **5.7.5** Treating physician judges continuation on the study would not be in the patient's best interest;
- **5.7.6** Patient becomes pregnant (pregnancy to be reported along same timelines as a serious adverse event);
- 5.7.7 Lost to follow-up. If a research subject cannot be located to document survival after a period of 2 years, the subject may be considered "lost to follow-up." All reasonable efforts must be made to locate subjects to determine and report their ongoing status. Lost to follow-up is defined by the inability to reach the subject after a minimum of three documented phone calls, faxes, or emails as well as lack of response by subject to one registered mail letter.

All attempts should be documented in the subject's medical records. If it is determined that the subject has died, the site will use permissible local methods to obtain the date and cause of death. If after all attempts, the subject remains lost to follow-up, then the last known alive date as determined by the investigator should be reported and documented in the subject's medical records.

6.0 ADVERSE EVENTS

6.1 Adverse Event Monitoring

The investigator or designee is responsible for ensuring that adverse events (both serious and non-serious) observed by the clinical team or reported by the subject which occur after the subject has initiated treatment and until the 30-day end-of-study visit, are fully recorded in the subject's medical records. Source documentation must be available to support all adverse events.

A laboratory test abnormality considered clinically relevant (e.g., causing the subject to withdraw from the study, requiring treatment or causing apparent clinical manifestations, result in a delay or dose modification of study treatment, or judged relevant by the investigator), should be reported as an adverse event.

The investigator or sub-investigator (treating physician if applicable) will provide the following for all adverse events (both serious and non-serious):

- Event term (as per CTCAE) Descriptions and grading scales found in the NCI Common Terminology Criteria for Adverse Events (CTCAE) version 5 will be utilized for AE reporting.
- Description of the event
- Date of onset and resolution
- Expectedness of the toxicity
- Grade of toxicity
- Attribution of relatedness to the investigational agent- (this must be assigned by an Investigator, sub-investigator, or treating physician)

- Action taken as a result of the event, including but not limited to; no changes, dose interrupted, reduced, discontinued, etc. or action taken with regard to the event. i.e. no action, received conmed or other intervention, etc.
- Outcome of event

All patients experiencing an adverse event, regardless of its relationship to study drug, will be monitored until:

- the adverse event resolves or the symptoms or signs that constitute the adverse event return to baseline
- any abnormal laboratory values have returned to baseline
- there is a satisfactory explanation other than the study drug for the changes observed, or
- death

6.2 Protocol-specific Adverse Event Monitoring Guidelines

Since this supplement is FDA approved as part of standard of care in the patient population under study, only AEs of interest, as outlined below, will be collected and recorded in the EDC:

- Any event deemed serious and expected OR unexpected, regardless of cause.

 AND
- AEs of interest included below:

Expected toxicities to Pancreaze
Abdominal pain
Abdominal pain upper
Flatulence
Diarrhea
Abnormal feces
Fatigue

Note; All expected toxicities from chemotherapy can be found in the FDA approved Package Insert.

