EOT End-of-Treatment FΑ Folinic Acid (Leucovorin) GLP-1 Glucagon-like peptide-1 H&P History & Physical Exam

HRPP Human Research Protections Program

IL1a Interleukin 1-alpha IV (or iv) Intravenously

MTD Maximum Tolerated Dose **LMF** Lipid Mobilizing Factors

LBM Lean Body Mass

NCI National Cancer Institute ORR Overall Response Rate

OS Overall Survival

PAWL Pancreatic Cancer-Associated Weight Loss

[figure not shown]
PBMCs Peripheral Blood Mononuclear Cells

PD Progression of Disease PFS Progression Free Survival

PR Partial Response

PYY Peptide YY

STUDY SCHEMA

Screening Phase

- 1. Informed consent
- 2. Screening
- 3. Eligibility review
- 4. Measure stool fecal elastase
- Measure fatsoluble vitamins

Treatment Phase

Cycle = 28 days

- 1. Measure weight stability
- 2. Assess 24-hour caloric intake
- 3. Assess stool frequency and consistency
- 4. Evaluate microbiome
- 5. Assess activity levels
- 6. Measure quality of life
- 7. Assess inflammatory biomarkers
- 8. Assess the presence of frailty phenotype
- 9. Assess body composition

End-of-Treatment

After C6D28:

- 1. Return pill bottles
- 2. Transition to Soc enzymes

Follow-up Phase

Safety evaluation

Measure fat-soluble vitamins

Survival

Optional sub-study: Followup activity tracking

STUDY SUMMARY

Title	Pancreatic-enzyme replacement therapy with pancreaze (pancrelipase) delayed-release in addition to standard of care for borderline resectable, locally advanced and advanced pancreatic adenocarcinoma patients (PANCAX-3) with cachexia and exocrine pancreatic insufficiency.		
Short Title	PANCAX-3		
Protocol Number	IIT2018-29-[name]-PNCX3		
Phase	Phase 2		
Methodology	Single arm, Single center		
Accrual Duration	18 months		
Study Duration	Approximately 6 months from screening to end of treatment assessment. Subjects will continue to be followed for survival for 36 months.		
Study Center(s)	Single-center, Cedars-Sinai Medical Center		
Objectives	 Feasibility to complete pancreatic enzyme replacement therapy at 8 weeks Measure weight stability at baseline and day 1 of every cycle for 6 months 24-hour caloric intake at baseline, C3D1, and end-of-study Stool frequency at baseline and C3D1 Quality of life assessment baseline and day 1 of every other cycle for 6 months Fitness tracking will be assessed with a wrist-worn wearable activity monitor (e.g., Fitbit Charge HR) continuously from day 1 of cycle 1 until the end of study visit. 		
Number of Subjects	Up to 40 patients (30 evaluable patients)		

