2.5.3 Exploratory endpoints

- Quality of life and symptoms of pain will be measured using the PROMIS-29 at baseline and day 1 of every cycle for 6 months
- Patient-reported response the therapy will be measured using FAACT at baseline and day 1 of every cycle for 6 months

- Measure fecal elastase at baseline
- Survival will be evaluated at every visit and every 6 months during 36month follow-up
- Safety and tolerability will be assessed by collecting adverse events throughout the study
- Research blood will be assessed for inflammatory biomarkers including: IL-6, interferon 1-alpha, TNF-alpha, Interleukin-1β, neuropeptide y, ZAG, ghrelin, CCK, GLP-1, PYY, glucagon and insulin at baseline and day 1 of every other cycle for 6 months and at the end-of-study visit. We will use standardized ranges for normal levels of the following assays.
- Presence of frailty phenotype using Fried's definition [50] will be evaluated
 at baseline and day 1 of every other cycle for 6 months by measuring
 patient grip strength, using a dynamometer during physical exam, a 15
 foot walk test, question about energy levels and activity (APPENDIX E)
- Assess body composition using computed tomography collected as standard of care every 8 weeks

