4.1.3 Dosing Delays / Modifications

Treatment is administered according to the Time & Events Table (Section 5.6). Treatment will be delivered over 4-week cycles (1 cycle=28 days). Data will also be collected for patients that receive titrated dosing per investigator's discretion and following Table 1.

Toxicity will be evaluated using the NCI Common Terminology Criteria for Adverse Events, Version 4.0. The frequency of toxicities per organ system will be tabulated using descriptive statistics. All patients who receive any amount of the study drug will be evaluable for toxicity.

Subjects will be instructed to take 84,000 units (4 capsules) per main meal and 42,000 units (2 capsules) per snack. Should dose reductions be required per treating investigator, the following guidelines will be followed:

Table 1. Dose modifications

	Per meal	Per snack
Starting dose	84,000 USP units of	42,000 USP units of
	lipase (4 capsules)	lipase (2 capsules)
Dose modification 1	63,000 USP units of 21,000 USP unit	
	lipase (3 capsules)	lipase (1 capsule)
Dose modification 2	42,000 USP units of	21,000 USP units of
	lipase (2 capsules)	lipase (1 capsule)

Any dose modifications will be recorded in the research record, including dates. Compliance will be calculated based on the recommended dose.

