4.2 Concomitant Medications

Concurrent use of other pancreatic enzyme supplementation, fat-soluble vitamin supplements, or over the counter supplements which contain lipase, protease, and amylase as active ingredients is not permitted.

Only conmeds that are used to treat an adverse event deemed at least possibly related to Pancreaze need to be recorded in the REDCap database.

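### The EDC takes only serious events and six listed toxicities, while the organ-system toxicity table and the tolerability endpoint are planned without that limit

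*Combined protocol and SAP*

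**What the plan says.** Section 6.2 restricts what enters the study database: "only AEs of interest, as outlined below, will be collected and recorded in the EDC". Two classes follow. The first is "Any event deemed serious and expected OR unexpected, regardless of cause". The second, introduced as "AEs of interest included below", is a list of six terms: abdominal pain, upper abdominal pain, flatulence, diarrhea, abnormal feces and fatigue. There is no line for other events, and no exception for events that are related, of high grade, or a cause of dose change or stopping.

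Other sections are written more broadly:

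- Section 4.1.3: "The frequency of toxicities per organ system will be tabulated using descriptive statistics", with the denominator "All patients who receive any amount of the study drug will be evaluable for toxicity".
- Section 2.5.3 (exploratory endpoints): "Safety and tolerability will be assessed by collecting adverse events throughout the study".
- Section 4.2: "Only conmeds that are used to treat an adverse event deemed at least possibly related to Pancreaze need to be recorded" in REDCap. This covers any event with that attribution, not just the six terms.
- Section 6.1: every adverse event, serious or not, goes into the medical records with grade, attribution, action taken and outcome. A laboratory abnormality that causes withdrawal or a dose modification is to be reported as an adverse event.

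Dose modifications and their dates go into the research record (4.1.3). Reasons for discontinuation are documented, and toxicity is one of those listed (5.7).

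**The concern.** The plan's safety output is wider than its safety input. A table by organ system implies that every organ system was observed. Under 6.2, five of the six listed terms are abdominal or bowel complaints and the sixth is fatigue. A non-serious event elsewhere in the body has no route into the EDC.

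What is at stake is how tolerability is described. The trial asks whether patients keep taking the capsules, so a reader will want to know which events led to a reduced or stopped dose. Section 4.5 replaces subjects who withdraw from study treatment, while 6.3.4 keeps anyone who took a dose in the safety analysis. The safety data are therefore a natural place to look for an account of those patients. The list also contains only expected toxicities, so an unexpected, related, non-serious event is among those left out.

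**Working it through.** No stated sample size, power or error rate bears on this point, so there is no figure in the plan to reproduce. The check follows each kind of event through the sections.

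| Kind of event | Medical records (6.1) | Other trace | EDC under 6.2 |
|---|---|---|---|
| Serious, any cause | Yes | Expedited reports (6.6.1) | Yes |
| Non-serious, one of the six terms | Yes | – | Yes |
| Unlisted, judged an important medical event (6.3.2.6) | Yes | – | Yes, if classed as serious |
| Unlisted, non-serious, at least possibly related, treated with a medicine | Yes | The medicine is in REDCap (4.2) | No |
| Unlisted, non-serious, leads to dose modification | Yes, with action taken | Modification and dates in the research record (4.1.3) | No |
| Unlisted, non-serious, leads to stopping | Yes, with action taken | Reason for stopping documented (5.7) | No |
| Non-serious laboratory abnormality that causes withdrawal or dose modification | Yes, as an adverse event | As in the two rows above | No |

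1. **What is missing.** In the last four rows the event itself is recorded at source, and part of its consequence is recorded elsewhere. The EDC lacks the term, the grade and the attribution.

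2. **Mismatch with 4.2.** In the fourth row the medicine is in the database and the event is not. The amendment log describes 6.2 as setting which events go into REDCap, so both rules appear to concern the same database.

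3. **Where the table draws its data.** Section 4.1.3 names no source. Section 10.7 sends required data to case report forms or a study database, and 6.2 is the only section that says which adverse events go there. No section plans to abstract the remaining events from the medical records for analysis. A table built from the EDC would therefore omit the last four rows.

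4. **Why the sections may disagree.** Section 4.1.3 still cites CTCAE version 4.0, while 6.1 and 6.4 use version 5. According to the log, the amendment to protocol version 4 both clarified the use of CTCAE version 5 and added Section 6.2. This suggests that the table plan was not revised when collection was narrowed.

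5. **Link to the primary endpoint.** Compliance comes from the patient's log (2.5.1) and uses no adverse event data. The lowest dose level in Table 1 is 42,000/84,000 = 50% of the starting dose per meal and 21,000/42,000 = 50% per snack. A patient who takes all of a reduced dose thus still reaches the 50% threshold, whether needed units are counted from the starting or the reduced dose. The gap affects how tolerability is explained and leaves the compliance result unchanged.

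**The case against.** The reduced collection is deliberate, and 6.2 gives the reason: the product is approved and part of standard care in this population. Patients also receive systemic chemotherapy, so many unlisted events would be hard to attribute to Pancreaze. Full details stay in the medical records and could be abstracted. Dose changes and reasons for stopping are documented, important medical events can be classed as serious, and an entered medicine would itself point to the event at source. Safety is exploratory. All of this stands. It justifies a short list and limits the weight of the point, but it does not reconcile 6.2 with 4.1.3, 2.5.3 and 4.2.

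A reader might go further in three ways that the documents do not support:

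- **That unlisted events are lost.** Section 6.1 requires them in the medical records with grade, attribution and action taken.
- **That the table will show zero for them, and that the zero will be read as an upper limit on their rate.** The plan does not name the table's source or say that rows will be printed for terms never collected. Only descriptive tabulation is planned, with no bound. No event rate is given from which to calculate a shortfall, and the denominator is all treated patients, with up to 40 enrolled, so it need not be the 30 evaluable.
- **That the primary result is compromised.** The compliance calculation does not use adverse event data.

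**Conclusion.** The inconsistency is real and worth correcting, at moderate priority. Followed as written, 6.2 leaves the EDC without the term, grade and attribution of unlisted non-serious events, including related ones and those that lead to a change or stop of Pancreaze. The conclusion that the table would omit them and understate toxicity rests on one assumption: that the table is built from the EDC. The documents name no other source. The amount of understatement cannot be estimated from the documents. The consequence is confined to the exploratory safety and tolerability assessment.

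**What to change.** Keep the reduced collection and make two changes.

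1. Extend 6.2 so that the EDC also takes (a) any non-serious adverse event that leads to interruption, reduction or discontinuation of Pancreaze, and (b) any adverse event judged at least possibly related to Pancreaze. Part (b) matches the rule already in 4.2, so each recorded medicine has its event.
2. State in 4.1.3 that the table draws on the EDC and is limited to the events collected under 6.2. Terms outside that scope should be shown as not collected rather than zero.

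The cost is transcription, because 6.1 already requires attribution and action taken at source. It may come to more than a few entries per patient, since attribution is difficult during concurrent chemotherapy and part (b) could bring in many events. If that load is too great, part (a) with the label is the smaller version, though the mismatch with 4.2 would remain. The label alone would prevent a misreading of the table, but the events behind dose changes and stops would still be outside the database. Neither change affects dosing, visits or clinical management.

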6.3 Definitions

6.3.1 Adverse Event

Any untoward medical occurrence associated with the use of a drug in humans, whether or not considered drug related. Therefore, an AE can be ANY unfavorable and unintended sign (including an abnormal laboratory finding), symptom, or disease temporally associated with the use of a medicinal (investigational) product, whether or not considered related to the medicinal (investigational) product (attribution of unrelated, unlikely, possible, probable, or definite). AE's will be collected once the consent is signed and treatment is initiated.

6.3.2 Serious Adverse Events

A "serious" adverse event is defined in regulatory terminology as any untoward medical occurrence that:

6.3.2.1 Results in death.

If death results from (progression of) the disease, the disease should be reported as event (SAE) itself.

6.3.2.2 Is life-threatening.

The patient was at risk of death at the time of the event; it does not refer to an event that hypothetically might have caused death if it were more severe.

- **6.3.2.3** Requires in-patient hospitalization or prolongation of existing hospitalization for \geq 24 hours.
- **6.3.2.4** Results in persistent or significant disability or incapacity.
- **6.3.2.5** Is a congenital anomaly/birth defect

6.3.2.6 Is an important medical event

Any event that does not meet the above criteria, but that in the judgment of the investigator jeopardizes the patient, may be considered for reporting as a serious adverse event. The event may require medical or surgical intervention to prevent one of the outcomes listed in the definition of "Serious Adverse Event."

Medical events may include, but are not limited to: allergic bronchospasm requiring intensive treatment in an emergency room or at home; convulsions that may not result in hospitalization; development of drug abuse or drug dependency.

